2. OBJECTIVES

Primary Objective: The primary objective of the Girls United cluster Randomized Controlled Trial (cRCT) is to examine the effectiveness of the Girls United prevention program on self-reported co-rumination.

Secondary Objectives: The second objective of this study is to investigate the intended active mechanisms of this program, especially enhancement of mindfulness and emotion regulation skills. Furthermore, the effectiveness of the Girls United mindfulness-based prevention program on self-reported symptoms of depression and anxiety, self-reported contagion of depression and anxiety symptoms, self- and friend-reported friendship quality, self-reported positive and negative affect, interpersonal responses to positive affect, self-reported self-worth

and parent-reported health care use will be studied in Dutch young adolescent girls from age 10 to 12 years old.

The research question is: To what extent does the app-based mindfulness prevention program Happy Friends, Positive Minds impact mental health and well-being in Dutch 10-to-12-year-old girls?

Hypotheses:

- (1) Girls in the intervention group will have a greater reduction in co-rumination (primary outcome) about distress and difficult emotions and feelings, (and thereby) internalizing symptoms (depression/anxiety, secondary outcome) and negative affect (secondary outcomes) during the intervention period, immediately after the intervention period and after one-year follow-up, relative to girls in the control condition.
- (2) Girls in the intervention group will have less dyadic depression contagion, immediately after the intervention period and after one-year follow-up, relative to girls in the control condition.
- (3) Girls in the intervention group will demonstrate less dyadic anxiety contagion during the intervention period, immediately after the intervention period and after one-year follow-up, relative to girls in the control condition.
- (4) Girls in the intervention group will experience better friendship quality, higher levels of positive affect and higher levels of interpersonal responses to positive affect, during the intervention period, immediately after the intervention period and after one-year follow-up, relative to girls in the control condition.

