4.4 Sample size calculation

Multi-level models are used with individuals nested in dyads. To determine the required sample size for this cRCT study power analyses were conducted using Optimal Design Plus – Evidence (Raudenbusch, 2011). These analyses were based on an alpha level (α) of .05, with three measurement points (baseline and two follow-up measurements), and an intraclass correlation (ICC) of .40 between two friends (ρ). This ICC was derived from observed ICCs for perceived support within friendship dyads ($n = 266$ pairs) in an existing dataset of adolescents with an average age of 13. For average risk girls (M), the multilevel power analysis was based on an expected effect size (Cohen's d) of 0.50, indicating a small to medium effect. The power analysis showed that, to achieve a power level of 0.80, at least 122 average-risk friendship dyads would need to be included. However, we will aim to oversample to a maximum of 160 dyads in order to be able to compensate for loss to follow up .

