10. STATISTICAL ANALYSIS

10.1 Primary study parameter(s)

To test the primary hypothesis, the following statistical analyses will be conducted:

Hypothesis 1 “Girls in the intervention group will have a greater reduction in co-rumination (primary outcome) about distress and difficult emotions and feelings, (and thereby) internalizing symptoms (depression/anxiety, secondary outcomes) and negative affect (secondary outcome) during the intervention period, immediately after the intervention period and after one-year follow-up, relative to girls in the control condition” will be tested via a multi-level (within level = girls within dyads; between level = dyads) parallel process, dual latent growth curve model (with co-rumination measured via self-report).

For analysis with co-rumination measured via self-report (T0 to one-year follow up T5), we will use multi-level parallel process, dual latent growth curve (LGM) models, with intervention arm as the exogenous predictor variable, growth rate of co-rumination (primary outcome) as the mediating variable and growth rate of internalizing symptoms as (correlated) secondary outcome variables. The mediator and primary and secondary outcome variables will be

modelled on both the individual (within) level and on the dyadic (between) level. This way, the between-level intervention effects will be adjusted for variation between individuals in co-rumination (primary outcome) and internalizing symptoms (depression/anxiety, secondary outcomes) at the within-level. Note that we have no a priori hypotheses regarding the nature of the growth patterns of the mediator and outcome variables and that they may be best captured by either a linear or a non-linear slope. We will adjust the analyses accordingly. For a (simplified) visual representation of this model, please see Figure 2. For a more technical description of this model, see Preacher, Zyphur, & Zhang, 2010; Preacher, Zhang, & Zyphur, 2011).

[figure not shown]

Figure 2. Simplified visual representation of a multilevel, duals process latent growth model with a predictor (e.g., intervention condition), mediator (e.g., co-rumination, primary outcome) and secondary outcomes (e.g., anxiety/depression). Ovals represent latent variables; squares represent observed variables. Double headed arrows represent (residual error) correlations, single headed arrows represent regression paths. Paths of interest are in bold.

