Hypothesis 4 “Girls in the intervention group will experience better friendship quality, higher levels of positive affect and higher levels of interpersonal responses to positive affect during the intervention period, immediately after the intervention period and after one-year follow-up, relative to girls in the control condition” will be tested using multi-level LGMs for each outcome, respectively.

Three multi-level LGMs with intervention arm as the exogenous predictor variable and growth rate of friendship quality, positive affect and interpersonal responses to positive affect as the (potentially correlated) outcome variables, will be used to test whether girls in the intervention arm experience more improvements in friendship quality, a faster growth in positive affect and faster growth levels of interpersonal responses to positive affect, compared to girls in the control arm. The outcome variables will be modelled on both the individual (within) level and

on the dyadic (between) level. This way, the between-level intervention effects will be adjusted for variation between individuals in the outcome measures on the within-level. Note that we have no a priori hypotheses regarding the nature of the growth patterns of the outcome measures and that it may best be captured by either a linear or a non-linear slope. We will adjust the analysis accordingly.

Hypothesis 5 “The hypothesized intervention effects on co-rumination (primary outcome) will be mediated by the development of mindfulness and emotion regulation skills during the intervention period, immediately after the intervention period and after one-year follow-up” will be tested using a multi-level parallel process LGMs for self-reported co-rumination.

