All analyses will be conducted in structural equation modeling program Mplus (v 8.7 or higher; Muthén and Muthén, 1998-2017). Model fit will be determined using the comparative fit index (CFI, critical value $\geq .95$), the root mean square error of approximation (RMSEA, critical value $\leq .06$) and the standardized root mean square residual (SRMR, critical value $< .08$; Hu & Bentler, 1999). When appropriate, standard errors will be adjusted for clustering of dyads within schools using a sandwich estimator (Williams, 2000). For hypotheses that include mediation analysis (hypothesis 1 & 5) we will use 10.000 bootstrap resamples with replacement and bias-corrected 95% confidence intervals to test these indirect effects (Preacher and Hayes, 2004). When appropriate, differences in (indirect) pathways between the intervention and the control arm will be estimated using the DIFFtest option in Mplus (when using the WLSMV estimator) or the Satorra Bentler chi-square difference test (Satorra & Bentler, 2001; when using the MLR estimator).

Handling of protocol non-adherence and missing data

The way the questionnaires are administered online makes it impossible to skip a question. Participants who do not complete a questionnaire will receive one or more reminders. Missing data during the follow-up period (e.g., due to unavailability during a certain measurement wave or due to dropout) will be handled using Full Information Maximum Likelihood (FIML) estimation.

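### Depression and anxiety: the protocol claims a greater reduction than under usual care, but the only test it names is the indirect effect through co-rumination, which does not test that claim

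*Protocol*

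**What the plan says.** **The claim.** Protocol section 2 gives the programme's mechanisms as one secondary aim and then, separately, its effectiveness on depression and anxiety symptoms. Hypothesis 1 predicts a greater reduction than among control girls in co-rumination ("and thereby) internalizing symptoms (depression/anxiety, secondary outcome) and negative affect (secondary outcomes").

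**The model.** Section 10.1 tests Hypothesis 1 with a multi-level parallel-process growth model. Arm is the predictor, with "growth rate of co-rumination (primary outcome) as the mediating variable and growth rate of internalizing symptoms as (correlated) secondary outcome variables". Negative affect is quoted as part of the hypothesis but does not appear in the description of this model.

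**The test.** Under the statistical software heading in section 10.2: "For hypotheses that include mediation analysis (hypothesis 1 & 5) we will use 10.000 bootstrap resamples with replacement", with bias-corrected 95% intervals for the indirect effects.

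**The contrast.** For Hypothesis 4 the same section specifies "Three multi-level LGMs with intervention arm as the exogenous predictor variable and growth rate of friendship quality", positive affect and interpersonal responses as outcomes. Hypothesis 6 has the same form for self-worth and health care use. Depression and anxiety have no such model.

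**The concern.** A greater reduction than in the control arm is a statement about the total effect of randomised arm. The indirect effect is a product: arm on co-rumination growth, times the association of co-rumination growth with symptom growth given arm. The second factor is not protected by randomisation. If arm moves co-rumination and the two slopes correlate for any other reason, the product is non-zero even when mean symptom change is identical in the two arms.

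The protocol makes that situation plausible. Section 1 describes co-rumination and internalizing problems as related, both concurrently and over time. It also says that only one component of co-rumination, dwelling on unpleasant feelings, goes with internalizing problems, while the others go with friendship quality, so the total score could fall without symptoms falling. Both constructs are self-reported by the same girls at the same waves (sections 8.1.1 and 8.1.2).

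At stake is a report that the programme reduces depression or anxiety when the randomised groups do not differ on either.

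**Working it through.** **1. Inputs from section 4.4.** The power analysis is "based on an alpha level (α) of .05" (two-sided assumed here), "to achieve a power level of 0.80", with Cohen's d "of 0.50, indicating a small to medium effect" and "an intraclass correlation (ICC) of .40 between two friends". It arrives at 122 dyads, with a maximum of 160.

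**2. The plan's own figure.** On dyad means, variance = (1 + 0.40)/2 = 0.70. Dyads per arm = 2 × (1.960 + 0.842)² × 0.70 / 0.50² = 43.96, so 44 per arm and 88 in total. With 61 per arm, power is 91%. The figure of 122 is not reproduced this way. It comes from a three-wave growth model whose variances are not given, so it cannot be rebuilt exactly. That is a separate matter and does not bear on this point; 122 and 160 are used below simply as the planned sizes.

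**3. Effect on the dyad scale.** 0.50 / √0.70 = 0.598 dyad-level SD.

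**4. Why the product is non-zero under a null total effect.** Let X be arm, M the co-rumination slope and Y the symptom slope, with unit residual variances:

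- M = −dX + e₁
- Y = r·e₁ + √(1 − r²)·e₂, so arm has no effect on Y

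Regressing Y on X and M gives path a = −d, path b = r, and a direct path of +rd. The indirect effect is −rd and the total is −rd + rd = 0. With d = 0.598 and r = 0.2, the indirect effect is −0.12, the direct effect +0.12 and the total 0.

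**5. Size.** Simulation at dyad level, 1,500 trials per cell, 600 bias-corrected bootstrap resamples each, true total effect on symptoms zero. The entries are the share of trials in which the indirect interval excludes zero. The correlation r is an assumption, because the protocol gives none.

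| Co-rumination effect (dyad SD) | Dyads | r = 0 | r = 0.1 | r = 0.2 | r = 0.3 | r = 0.5 |
|---|---|---|---|---|---|---|
| 0.598 (d = 0.50) | 122 | 8% | 25% | 62% | 87% | 92% |
| 0.598 (d = 0.50) | 160 | 8% | 29% | 74% | 96% | 97% |
| 0.25 | 122 | 3% | 9% | 26% | 32% | 32% |
| 0.25 | 160 | 3% | 14% | 33% | 41% | 40% |
| 0 | 122 | 0.5% | 2% | 5% | 9% | 6% |
| 0 | 160 | 0.5% | 3% | 7% | 9% | 8% |

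The ordinary comparison of symptom slopes between arms rejects in about 5% of trials throughout (4–7%).

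**6. Checks.**

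- By hand, at 160 dyads and r = 0.2, both paths must be significant. Path a: z = 0.598/(2/√160) = 3.78, power 0.97. Path b: z = 0.2 × √157/√0.96 = 2.56, power 0.73. The product is about 0.70; the bias-corrected interval is somewhat more liberal, consistent with the simulated 74%.
- A separately written simulation at d = 0.5 and r = 0.1, 0.2 and 0.3 gave 23, 64 and 87% at 122 dyads and 28, 75 and 96% at 160.
- A version with six waves (months 0, 2, 4, 6, 8 and 20), fitted slopes and observed slope correlations of about 0.13, 0.20 and 0.30 gave 32, 64 and 93% at 122 dyads and 46, 82 and 97% at 160.
- Leaving the direct path out of the fitted model at 122 dyads gave nearly the same rates (23, 61 and 87% at r = 0.1, 0.2 and 0.3).

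**The case against.** The strongest reply is that Hypothesis 1 is itself mediational. It ties the symptom reduction to the co-rumination reduction, so a mediation model suits it. Section 10.2 says that the hypothesis includes mediation, not that the indirect effect alone decides it. Section 10.1 speaks of intervention effects in the plural, and the fitted model can yield direct and total effects. Figure 2, which is not reproduced in the text available here, may draw a direct path from arm to symptoms. Section 10.2 also mentions a growth model and survival analysis under Hypothesis 3, and survival analysis under Hypothesis 2. Which coefficients are reported could be left to a statistical analysis plan.

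Much of this stands. A reader might infer that the indirect effect is the only test planned. The text supports only that it is the only test named. The wording of the hypothesis also justifies a mediation analysis.

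It does not remove the point. The secondary objective on depression and anxiety carries no mediational wording, and Hypothesis 1 still makes a comparison with control. A direct path in Figure 2 would not be the total effect either. The extra methods under Hypotheses 2 and 3 belong to contagion and are not described. This is therefore not detail left open: a test is stated, and it does not match the claim.

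A reader might also infer that the indirect test is wrong in most trials whenever the programme leaves symptoms unchanged. The documents do not support that. The high rates need both a co-rumination response and slopes correlated for other reasons.

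**Conclusion.** The point holds as a mismatch between claim and named test for depression and anxiety, with negative affect omitted from the 10.1 model as an additional gap. It concerns these secondary outcomes; the arm effect on co-rumination, the primary outcome, is not called into question by it.

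The size is conditional. With a co-rumination effect of about d = 0.5 and within-arm slope correlations of 0.1 to 0.3, the indirect interval excludes zero in roughly 23–87% of trials at 122 dyads and 28–96% at 160, with no arm difference in symptoms. At a co-rumination effect of 0.25 dyad SD and correlations of 0.1 to 0.5, the range is 9–41%. If co-rumination does not respond, or the slopes are uncorrelated, it is at most about 9%. The correlations and the exactly zero symptom effect are assumptions, and dyad-level slopes stand in for the two-level latent model. The unfavourable case is nonetheless the one in which the trial succeeds on its primary outcome at the effect size used for its power calculation.

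The protocol does not say that a significant indirect effect will be reported as symptom reduction. It leaves that conclusion open and names no test that would guard against it.

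**What to change.** In section 10.1:

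- Name the total effect of arm on the growth of depression, anxiety and negative affect, in the multi-level growth-model form already used for Hypothesis 4, as the test of effectiveness on these outcomes.
- Keep the indirect effect through co-rumination as the mechanism analysis, reported beside the total and direct effects.
- State that a reduction in symptoms will not be claimed from the indirect effect alone.

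The cost is wording and one further reported coefficient per outcome, with no new data. The downside is that a claim of symptom reduction becomes harder to make than under the indirect test.

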3. STUDY DESIGN

Design

The Girls United cRCT aims to evaluate the effectiveness of the Girls United program, a school-based intervention blending targeted mindfulness and psychoeducation. Delivered by trained and experienced mindfulness health professionals, the program is compared to a teaching-and-care-as-usual (TAU) approach. The study includes two groups: (1) an intervention group where girls' friendship dyads participate in the Girls United program, and (2) a control group where girls' friendship dyads receive TAU.

Duration

The 14-week Girls United program will be delivered in two cohorts across two academic years: cohort 1 in 2025–2026 and cohort 2 in 2026–2027. The program will run in four phases from October 2025 to May 2026 for both cohorts. Baseline measurements (T0) will occur in September 2025 for cohort 1 and February 2026 for cohort 2. Subsequent measurements include T1 (November 2025 for cohort 1 and April 2026 for cohort 2), T2 (January 2026 for cohort 1 and June 2026 for cohort 2), T3 (March 2026 for cohort 1 and October 2026 for cohort 2), and T4 post-intervention measurements (May 2026 for cohort 1 and December 2026 for cohort 2). A long-term follow-up measurement (T5) will be conducted in May 2027 for cohort 1 and December 2027 for cohort 2 (see Figure 1).

Setting

The study will take place at mainstream primary schools of school partnerships such as RiBA, BLICK op onderwijs and Scholennetwerk BSI and schools that are involved via our social media channels and webinars. These schools will be broadly representative of Dutch mainstream primary schools with respect to the type of school (urban/rural, large/small) and high/middle/low Socio Economic Status (SES) of the school.

[figure not shown]

Figure 1. Flowchart of study assessment time points for cohort 1 and 2.

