8.2 Randomisation, blinding and treatment allocation

Dyads will be randomly assigned in a 1:1 ratio to either the intervention group (max 80 dyads; $n = \text{max } 160$ girls) or the control group (TAU; max 80 dyads; $n = \text{max } 160$ girls) by an independent researcher using CASTOR EDC, a web-based randomization program compliant with Good Clinical Practice (GCP) guidelines. Ideally, randomization will occur on a single day after completing the screening phase. If this is not feasible (e.g., due to time constraints), randomisation will proceed in batches of 50 dyads (100 girls) and on classroom level. The median of the screening scores will be calculated, and dyads where one or both girls above the median will be included. These dyads will then be randomly assigned to the intervention or control group using a block randomisation procedure (50% allocated to each group). Allocation will be concealed through a computer-generated list in a secure web-based application. However, due to the organisational structure of the prevention program, participants, parents, schools, and researchers will be aware of group assignments. As the trial follows an open-label design, unblinding will not occur.

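### The primary test of co-rumination rests on a T0–T5 growth rate whose shape is left to the data, and no coefficient or time point is named to carry it

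*Protocol*

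**What the plan says.** Section 10.1 states Hypothesis 1 for three periods: "during the intervention period, immediately after the intervention period and after one-year follow-up, relative to girls in the control condition". The stated analysis is a multilevel parallel-process latent growth model over T0 to T5. Arm is the predictor, with "growth rate of co-rumination (primary outcome) as the mediating variable and growth rate of internalizing symptoms" as correlated secondary outcomes. The effect on the primary outcome is therefore the path from arm to that growth rate.

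The same section says there is no prior hypothesis about the growth pattern of mediator or outcomes, and that "they may be best captured by either a linear or a non-linear slope. We will adjust the analyses accordingly". It gives no time scores, no breakpoint at T4, no rule for selecting the shape and no contrast at any wave. The fit cut-offs (CFI, RMSEA, SRMR) under the statistical software heading of Section 10.2 are not presented as a rule for choosing the shape.

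Section 8.2 says that participants, parents, schools and researchers will know the allocation.

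Section 3 (Duration) sets T0 to T5 at September 2025 to May 2027 for cohort 1 and February 2026 to December 2027 for cohort 2, with "T3 (March 2026 for cohort 1 and October 2026 for cohort 2". It also states: "The program will run in four phases from October 2025 to May 2026 for both cohorts".

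**The concern.** A claim about three periods needs either three contrasts or a stated rule that ranks them. Here there is one growth parameter, and its meaning changes with the shape chosen. Under a linear form it is an average rate over 20 or 22 months. Under a quadratic, piecewise or free-loading form there are several growth coefficients, and the protocol does not say which one decides the primary hypothesis.

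This goes beyond detail left for a later document. The protocol commits the primary analysis to being adapted to the observed growth pattern, in a trial where the researchers know the arms. If the effect changes after the programme ends, which is plausible for any prevention programme, the candidate analyses can reach opposite conclusions from the same data.

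**Working it through.** **The plan's own figure.** Section 4.4 gives 122 dyads for d = 0.50, ICC 0.40, alpha .05, power 0.80 and three measurement points. The standard two-mean formula gives 63 girls per arm. Multiplied by 1 + 0.40 this is 88.2 girls per arm, or about 88 dyads in total. The 122 is not reproduced, but the software settings are not stated, so this does not show it to be wrong. I use it only to set 61 dyads per arm. The calculation assumed three measurement points whereas the model uses six, so power has not been shown for the planned test.

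**Inputs from the protocol.** Months since T0, from Section 3: cohort 1 at 0, 2, 4, 6, 8, 20; cohort 2 at 0, 2, 4, 8, 10, 22. ICC 0.40 and d = 0.50 from Section 4.4.

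**Assumptions.** The arm effect builds linearly to -0.50 SD at T4, and a fraction k of it remains at T5. Between-wave correlation r is 0.5 to 0.7, variances are equal, the test is two-sided at 0.05, and all 61 dyads per arm follow one cohort's times. The variance of a dyad mean is (1 + 0.40)/2 = 0.7.

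**Linear slope in months.** Slope difference = Sxy/Sxx; SE = sqrt(2 × 0.7 × (1 − r)/(61 × Sxx)); probability of showing benefit = Φ(−slope/SE − 1.96).

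- Cohort 1: mean time 6.67, Sxx = 253.3. T5 alone supplies 13.33² = 177.8 of this, or 70%. Sxy = 0.833 − 6.667k. The SE is 0.00673 (r = 0.5) or 0.00521 (r = 0.7).
- Cohort 2: mean time 7.67, Sxx = 315.3, T5 share 65%. Sxy = 0 − 7.167k. The SE is 0.00603 or 0.00467.

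| Kept at T5 | Cohort 1 slope per month | Implied T4 effect (8 × slope) | P(benefit), cohort 1 | P(benefit), cohort 2 |
|---|---|---|---|---|
| all | -0.0230 | -0.18 SD | 93–99% | 96–99.8% |
| half | -0.0099 | -0.08 SD | 31–47% | 47–68% |
| none | +0.0033 | +0.03 SD | under 1% | 2.5% |

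**Linear slope by wave number (0 to 5).** Sxx = 17.5 and the SE is 0.0256 or 0.0198. On the cohort 1 path, Sxy = −0.625 − 1.25k. With none kept the slope is −0.0357 and the probability 29–44%; with half kept it is −0.0714 and 80–95%.

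**Quadratic in months, change from T0 to T4.** The least-squares quadratic fitted to the fully faded path gives −0.49 SD at T4 in both cohorts. For cohort 1 the SE is 0.134 or 0.104, giving 95–99.7%. For cohort 2 it is 0.129 or 0.100, giving 97–99.8%.

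**Direct T4 contrast.** Unadjusted: SE = sqrt(1.4/61) = 0.151, power 91%. Adjusted for baseline: SE = sqrt(1.4 × (1 − r²)/61), power 97–99.6%. Neither depends on what happens at T5.

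**Sensitivity.** A generalised least-squares version was run with assumed variances (intercept 0.5, residual 0.4, slope 0 or 0.1 at T5) and 122 or 160 dyads in total. With baseline means constrained equal across arms, a fully faded effect is detected with about 3% (cohort 1 months), 8–10% (cohort 2 months) or 52–72% (wave number). The dependence on time coding remains.

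**The case against.** The strongest reply is that the protocol expressly permits a non-linear form, and a fading effect is exactly the case in which a linear form fits badly and another would be preferred. The quadratic figures bear this out: that permitted model performs about as well as a direct T4 contrast. A reader might infer that the planned analysis cannot answer Hypothesis 1, or would miss an effect that fades by one year. The documents do not support that. It holds only if a linear slope in calendar months is chosen.

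Three further inferences also go too far.

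- That one set of time scores will be wrong for one cohort: the protocol states no time scores, and cohort-specific or individual times are compatible with it.
- That T0 is measured after allocation is known: Section 8.2 says that ideally "randomization will occur on a single day after completing the screening phase", but it does not order T0 against randomisation, and the assessment flowchart (Figure 1) is not shown.
- That placing co-rumination as mediator biases the primary effect: the path from arm to its growth is still the total arm effect on that growth.

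Time scores and wave contrasts are commonly left to a statistical analysis plan, and one may exist. Their absence alone is no fault. What stands is that the protocol is not silent: it prescribes adapting the primary model to the observed pattern and names no deciding parameter.

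**Conclusion.** The point holds in this form: the primary estimand and its test are not fixed, and the protocol prescribes a data-led choice of shape in an open-label trial. The choice can decide the result. For an effect of -0.50 SD at T4 that is gone at T5, the probability of showing benefit runs from under 1% to 99.8% across analyses the text allows. If half is kept, a linear slope gives 31–47% (cohort 1 months), 47–68% (cohort 2 months) or 80–95% (by wave, cohort 1 path). If all is kept, every option detects an effect, but a linear slope in months implies only -0.18 SD at T4 in cohort 1.

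The effect path and the between-wave correlations are assumptions, so these figures show how far the choice matters; they do not predict the trial's power. The date conflict in Section 3 is a real but separate contradiction and does not bear on this conclusion.

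**What to change.** Replace the data-led sentence in Section 10.1 with a pre-specified primary contrast: the arm difference in CRQ-Short at T4, then at T5, tested in that fixed order. Estimate both from a categorical-time model, or from a growth model with a fixed knot at T4. Use actual months since T0, include dyad and girl effects, and adjust for cohort and the pre-allocation screening CRQ-Short score. The screening score avoids having to settle whether T0 precedes allocation. A replacement friend recruited under Section 8.4 may have no such score, so that case needs a stated rule. Keep the parallel-process mediation model as a secondary analysis.

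The cost is protocol wording, with no new data collection. The small downside is that the mediation model is no longer the primary test.

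Separately, reconcile Section 3: the programme is said to run from October 2025 to May 2026 for both cohorts, while cohort 2 has T0 in February 2026 and its post-intervention T4 in December 2026.
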